3.10.4.2 Concurrent medical procedures

Concurrent medical procedures will be attributed to study periods based on the start date of the procedure. Study periods are as defined in Section 3.2.3.

3.10.4.3 Additional healthcare provider visits

Healthcare provider consultations not foreseen by the protocol will be attributed to study periods based on the date of consultation.

3.10.4.4 Hospital stays

Hospital stays will be attributed to study periods based on admission date.

The duration of each hospital stay will be calculated as discharge date minus the admission date (Hospitalization Visit Date on the CRF) plus 1 day for hospital stays with a discharge date.

The durations of hospital stays will be summed within each of the Evaluation, Down-Titration, and Safety study periods. Subjects with no hospital stays within a study period will have a duration of 0 days for that period. Should distinct records for hospital stays overlap, then the days during the overlap will only be counted once.

Hospital stay durations will be categorized as follows: 1 day, 2-5 days, 6-10 days, 11-15 days and >15 days.

3.10.4.5 Emergency room visits

Emergency room (ER) visits will be attributed to study periods based on admission date.

The duration of each ER visit will be calculated as discharge date minus the admission date (ER Visit Date on the CRF) plus 1 day for emergency room visits with a discharge date.

Both ER visits that result in a subsequent hospital stay and ER visits that do not result in a subsequent hospital stay will be counted.

3.10.5 Questionnaire data

For all questionnaire data where different languages or terminology is used between patients, the differences in questionnaires will be reviewed in a blinded manner prior to database lock in order to determine whether responses may be grouped.

3.10.5.1 Achenbach CBCL

The Achenbach CBCL form is a questionnaire intended to evaluate a child's competencies and behavioral/emotional problems. Depending on the subject's age, 1 of 2 versions of the Achenbach CBCL is used. The Achenbach CBCL/1½-5 checklist is intended for use in children aged between 18 months and 5 years and 11 months. For subjects between 6 years and < 17 years, the Achenbach CBCL/6-18 version is used. The Achenbach CBCL is not applied to children below 18 months of age.

The CBCL/1½-5 checklist comprises 100 questions and the CBCL/6-18 checklist comprises 120 questions with the response options of:

- 0=not true (as far as known)

- 1=somewhat or sometimes true
- 2=very true or often true

The CBCL/1½-5 checklist will be grouped according to syndrome scales according to [Table 3–8](#) and the CBCL/6-18 checklist will be grouped according to the empirically based syndrome scales in [Table 3–9](#).

Table 3–8: CBCL/1½-5 checklist

Syndrome scale	Questions
Aggressive behavior	8, 15, 16, 18, 20, 27, 29, 35, 40, 42, 44, 53, 58, 66, 69, 81, 85, 88, 96
Anxious / depressed	10, 33, 37, 43, 47, 68, 87, 90
Attention problems	5, 6, 56, 59, 95
Emotionally reactive	21, 46, 51, 79, 82, 83, 92, 97, 99
Sleep problems	22, 38, 48, 64, 74, 84, 94
Somatic complaints	1, 7, 12, 19, 24, 39, 45, 52, 78, 86, 93
Withdrawn	2, 4, 23, 62, 67, 70, 71, 98

Table 3–9: CBCL/6-18 checklist

Syndrome scale	Questions
Aggressive behavior	3, 16, 19, 20, 21, 22, 23, 37, 57, 68, 86, 87, 88, 89, 94, 95, 97, 104
Anxious / depressed	14, 29, 30, 31, 32, 33, 35, 45, 50, 52, 71, 91, 112
Attention problems	1, 4, 8, 10, 13, 17, 41, 61, 78, 80
Rule-breaking behavior	2, 26, 28, 39, 43, 63, 67, 72, 73, 81, 82, 90, 96, 99, 101, 105, 106
Social problems	11, 12, 25, 27, 34, 36, 38, 48, 62, 64, 79
Somatic complaints	47, 49, 51, 54, 56a, 56b, 56c, 56d, 56e, 56f, 56g
Thought problems	9, 18, 40, 46, 58, 59, 60, 66, 70, 76, 83, 84, 85, 92, 100
Withdrawn / depressed	5, 42, 65, 69, 75, 102, 103, 111

The sum of the raw score of values within each syndrome scale will be calculated for each subject according to the questionnaire used.

Standardized T-scores are determined from each subject's raw syndrome score based on the subject's age and sex. Tables mapping each raw score to the appropriate T-score are provided in the CBCL Professional Manual and will be reproduced programmatically.

Further T-scores will be categorized with regard to clinical significance (CS) to summarize categorical shift from Baseline. The legacy categories for CS are defined as follows:

- If T-score is < 65 then CS category = “Normal”
- If T-score is 65 - < 70 the CS category = “Borderline”

- If T-score is ≥ 70 then CS category = “Clinically Significant”.

T-scores will also be categorized using the dichotomous approach with regard to CS to summarize categorical shift from Baseline. The categories for CS are defined as follows:

- If T-score is < 65 then CS category = “Normal”
- If T-score is $65 \leq$ the CS category = “Borderline or Clinical Range”

Achenbach CBCL will be conducted at ScrV, EV (for DE and LTFU subjects respectively), at FEVs, YEVs and FV/EDV. The version of the Achenbach CBCL appropriate to each subject’s age should be administered with the following exception: If a subject completed the Achenbach CBCL/1½-5 at the Baseline assessment and turns 6 years of age between that assessment and the initial YEV, the CBCL/1½-5 should be completed through and including the initial YEV, and subsequently the CBCL/6-18 should be completed. Moreover, if a subject was below 18 months of age at Baseline but turns ≥ 18 months between Baseline and initial YEV, Achenbach CBCL/1½-5 will be assessed at visits after initial YEV.

The change from Baseline will be calculated using T-scores and raw scores by subtracting the Baseline result (ScrV or EV) from the post-Baseline visit result:

$$\text{Change from Baseline} = \text{Score at postBaseline visit} - \text{Score at Baseline}$$

at each visit in the Evaluation Period, if Baseline value is available. A decrease from Baseline (change from Baseline < 0) indicates improvement in behavior, while an increase (change from Baseline > 0) indicates worsening.

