9.4 Achenbach Child Behavior Checklist

The Achenbach CBCL is completed at the ScrV (DE subjects only), FEV, YEV, FV, and at the EDV in the case of early discontinuation. For LTFU subjects (except for those from core studies EP0065 and N01349), at the EV, the Achenbach CBCL score is obtained from the Baseline of the core study and should not be recorded in the eCRF for N01266. For DE subjects, the Achenbach CBCL completed at the ScrV and for EP0065 LTFU subjects the Achenbach CBCL completed at the EV, will be the Baseline assessment. For LTFU subjects from core study N01349 Achenbach CBCL Baseline assessment is not available, as this questionnaire was not performed in core study N01349 and not recorded at EV in N01266 study.

Calculated T-score values and raw score values and the corresponding change from Baseline for each CBCL/1½-5 syndrome (aggressive behavior, anxious / depressed, attention problems, emotionally reactive, sleep problems, somatic complaints, withdrawn) will be summarized for each scheduled visit during the Evaluation Period if available.

Calculated T-score and raw score values and corresponding change from Baseline for each CBCL/6-18 syndrome (aggressive behavior, anxious / depressed, attention problems, rule-breaking behavior, social problems, somatic complaints, thought problems, and withdrawn / depressed) will be summarized for each scheduled visit during the Evaluation Period if available.

Additionally, for all CBCL/1½-5 syndromes as well as CBCL/6-18 syndromes, shift tables for T-scores will be done. These shift tables are based on T-score legacy categorization “Normal”, “Borderline” or “Clinical Significant” and the dichotomous approach “Normal” or “Borderline or Clinical Range” as described in Section 3.10.5.1 and will summarize the shift from Baseline for each visit during the Evaluation Period if available and for the last assessment. These shift tables will not include LTFU subjects from core studies N01349 as Baseline values are not available from this study.

All Achenbach CBCL data will be listed. Data assessed on unscheduled visits will be included in listings only.

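### The CBCL change-from-Baseline rule has no same-version condition, so as written it does not exclude subtracting a CBCL/1½-5 raw score from a CBCL/6-18 raw score of different length

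*SAP*

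**What the plan says.** SAP Section 3.10.5.1 uses two CBCL versions, chosen by age. The raw score is a simple item sum, with each item scored 0 to 2: "The sum of the raw score of values within each syndrome scale will be calculated for each subject according to the questionnaire used". Tables 3-8 and 3-9 list the items of each scale.

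A child who starts on the younger form changes form on reaching age 6. One who turns 6 before the initial yearly visit keeps the younger form a little longer: "the CBCL/1½-5 should be completed through and including the initial YEV, and subsequently the CBCL/6-18 should be completed".

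The change rule follows at once and covers both versions: "The change from Baseline will be calculated using T-scores and raw scores by subtracting the Baseline result (ScrV or EV") from the post-Baseline result. It is to be applied "at each visit in the Evaluation Period, if Baseline value is available. A decrease from Baseline (change from Baseline < 0) indicates improvement in behavior"; an increase is read as worsening. Availability of a Baseline is the only condition.

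Section 9.4 has one reporting paragraph per version. For the older form it asks for "Calculated T-score and raw score values and corresponding change from Baseline for each CBCL/6-18 syndrome", by scheduled visit. It says that subjects from N01349 have no CBCL Baseline and leaves them out of the shift tables. It does not mention children who change version.

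**The concern.** The two versions are different questionnaires that share scale names. Four names are identical: Aggressive behavior, Anxious/depressed, Attention problems and Somatic complaints. A fifth pair is close (Withdrawn; Withdrawn/depressed). A raw sum depends on how many items are added up, so a difference between sums of different length mixes any change in behavior with the change of form.

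A child who has switched does have a Baseline at ScrV or EV, so the rule's only condition is met. A programmer who matches on subject and scale name would compute post minus Baseline across versions. The sign convention would then label the length difference as improvement or worsening. With a single arm there is no control group in which the same artefact would appear and be recognized. It would fall at later visits, after children have aged into the older form.

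**Working it through.** **1. Is a same-version condition written anywhere?**

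| Place in the SAP | What it fixes | Same version required? |
|---|---|---|
| 3.3, general Baseline rule | Which measurement in time is Baseline | Not stated |
| 3.10.5.1, change rule | Post minus Baseline, raw and T-score, if Baseline is available | Not stated |
| 9.4, summaries | Separate paragraphs for each version's syndromes | Not stated |
| 9.4, shift tables | N01349 left out for lack of a Baseline | Switchers not mentioned |
| 3.10.5.2 and 3.10.5.3, BRIEF and BRIEF-P | Change formula for each form | Yes: the form is named on both sides |

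The CBCL formula is generic where the BRIEF and BRIEF-P formulas are form-specific.

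**2. Item counts, from Tables 3-8 and 3-9.** For example, Aggressive behavior is "8, 15, 16, 18, 20, 27, 29, 35, 40, 42, 44, 53, 58, 66, 69, 81, 85, 88, 96" on the younger form (19 items) and "3, 16, 19, 20, 21, 22, 23, 37, 57, 68, 86, 87, 88, 89, 94, 95, 97, 104" on the older (18 items). Anxious/depressed on the younger form is "10, 33, 37, 43, 47, 68, 87, 90" (8 items), against 13 on the older. Maximum raw score = 2 × items.

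| Scale | CBCL/1½-5 items (max) | CBCL/6-18 items (max) | Difference in items |
|---|---|---|---|
| Attention problems | 5 (10) | 10 (20) | +5 |
| Anxious/depressed | 8 (16) | 13 (26) | +5 |
| Aggressive behavior | 19 (38) | 18 (36) | −1 |
| Somatic complaints | 11 (22) | 11 (22) | 0 |
| Withdrawn; Withdrawn/depressed | 8 (16) | 8 (16) | 0 |

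Three of the four identically named scales differ in length. The two pairs of equal length have different item lists on the two versions.

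**3. Size of the length artefact.** The plan gives no figure to reproduce and no item means. Assume the mean item score m is the same before and after the switch. Then

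false raw change = m × (items in CBCL/6-18 − items in CBCL/1½-5).

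| Assumed m | Attention problems | Anxious/depressed | Aggressive behavior |
|---|---|---|---|
| 0.25 | 0.25 × 5 = +1.25 | +1.25 | 0.25 × (−1) = −0.25 |
| 0.5 | 0.5 × 5 = +2.5 | +2.5 | −0.5 |
| 1 | 1 × 5 = +5 | +5 | −1 |
| 2 (ceiling) | 2 × 5 = +10 | +10 | −2 |

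At m = 1 the Attention problems score goes from 5 to 10 with no change in the average response. Somatic complaints shows 0 at every m.

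**4. Who can be affected.** A child aged 5 at Baseline turns 6 within a year, keeps the younger form through the month 12 visit and, by Table 2-1, meets the older form at the next full evaluation (month 18). A child aged exactly 3 at Baseline reaches 6 only at 36 months. Section 2 sets at least 3 years of treatment but adds other end points, whichever comes first. The SAP gives no number of children in this age range, so the share of change values affected cannot be calculated.

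**The case against.** The best defense is that the plan can be read as form-specific. Section 9.4 reports each version separately, raw scores follow the questionnaire used, and the general Baseline rule for directly enrolled subjects in Section 3.3 refers to the corresponding outcome. On that reading a child with a CBCL/1½-5 Baseline has no CBCL/6-18 Baseline, so no change is calculated after the switch. Holding the Baseline form through the initial yearly visit also suggests that continuity of form was in mind.

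This reading is plausible and it stands in part. A reader might infer from the change rule that the plan orders cross-version subtraction; it does not say so. But the defense is not written either. The change rule ties Baseline to a visit, not to a version, and the only subjects described as lacking a CBCL Baseline are those from N01349. Two competent programmers could produce different tables.

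Four further limits stand:

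- A reader might infer that every like-named scale is distorted by length. Somatic complaints has 11 items on both versions.
- The point sizes rest on an assumed common item mean across different items answered at different ages.
- A reader might extend the argument to T-scores and the shift tables. T-scores are standardized by age and sex, and the shift tables use T-scores only; the item-count argument concerns raw scores.
- A reader might infer that most children aged 3 to 5 are affected, or that the main long-term results are at risk. The documents give no such count. The primary variables are adverse events; the CBCL is among the other variables, summarized descriptively without testing.

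**Conclusion.** The point holds as an omission with a wrong result under a literal reading. The change rule does not exclude cross-version subtraction, a within-subject change of version is planned, and three of the four identically named raw scales differ in length.

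If cross-version raw change were calculated and the mean item score stayed at an assumed 0.5 to 1, Attention problems and Anxious/depressed would each show a false worsening of 2.5 to 5 raw points, and Aggressive behavior a false improvement of 0.5 to 1. If the tables are programmed with a version-specific Baseline, the artefact is zero, but the plan would still not say how children who switched are shown. The effect on any visit mean depends on an unknown number of switchers. Importance is minor to moderate.

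**What to change.** Add to SAP Section 3.10.5.1, and apply in Section 9.4: raw-score change from Baseline is calculated only when the Baseline and post-Baseline assessments used the same CBCL version; after a switch, CBCL/6-18 raw scores are shown as observed values only. This removes the item-count artefact on every scale.

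Separately, state whether T-score change and shift from Baseline are shown across versions. This is the sponsor's choice; if it is done, flag those values as cross-version.

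The cost is one or two sentences and a version check in the programs. The downside is fewer raw change values at late visits, because children who have switched no longer contribute one.

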3.10.5.2 BRIEF scores

The BRIEF form is a questionnaire entered for subjects ≥ 5 years of age to assess subjects’ executive functioning. Executive functions broadly encompass a set of cognitive skills that are responsible for the planning, initiation, sequencing, and monitoring of complex goal-directed behavior.

The BRIEF form should be used for subjects ≥ 5 years of age, and within the following exception: for subjects who completed the BRIEF-P at Baseline assessment and turns 5 years of age between that assessment and the initial YEV, the BRIEF-P should be completed through and including initial YEV, and subsequently the BRIEF should be completed.

The questionnaire comprises 86 questions with entry options of N (never; scored as 1 point), S (sometimes; scored as 2 points) and O (often; scored as 3 points). Higher scores reflect poorer functioning. The questions are categorized in 8 components: Inhibit, Shift, Emotional Control, Initiate, Working Memory, Plan/Organize, Organization of Materials and Monitor. Additionally, three subscales will be used to calculate subscale scores.

[Table 3–10](#) presents which questions belonging to which component and the constitution of subscales.

Table 3–10: BRIEF components and subscales

Scale/Index	Questions
Inhibit	38, 41, 43, 44, 49, 54, 55, 56, 59, 65
Shift	5, 6, 8, 12, 13, 23, 30, 39

Scale/Index	Questions
Emotional Control	1, 7, 20, 25, 26, 45, 50, 62, 64, 70
Initiate	3, 10, 16, 47, 48, 61, 66, 71
Working Memory	2, 9, 17, 19, 24, 27, 32, 33, 37, 57
Plan/Organize	11, 15, 18, 22, 28, 35, 36, 40, 46, 51, 53, 58
Organization of Materials	4, 29, 67, 68, 69, 72
Monitor	14, 21, 31, 34, 42, 52, 60, 63
BRI	All questions from Inhibit, Shift, and Emotional Control
MI	All questions from Initiate, Working Memory, Plan/Organize, Organization of Materials, and Monitor
GEC Score	Questions 1-72

BRI=Behavioral Regulation Index, MI=Metacognition Index, GEC=Global Executive Composite.

Standardized T-scores are determined from each subject's raw GEC, BRI, MI, and component scores based on the subject's age and sex. Tables that map each raw score to the appropriate T-score are provided in the BRIEF Professional Manual and will be reproduced programmatically.

In addition, T-scores will be categorized with regard to CS to summarize categorical shift from Baseline. The legacy categories for CS are defined as follows:

- If T-score is 0 - < 50 then CS category = "Normal"
- If T-score is 50 - < 65 the CS category = "Borderline"
- If T-score is >= 65 then CS category = "Clinically Significant".

T-scores will also be categorized using the dichotomous approach with regard to CS to summarize categorical shift from Baseline. The categories for CS are defined as follows:

- If T-score is < 65 then CS category = "Normal"
- If T-score is >= 65 then CS category = "Potentially Clinically Significant".

Two validity scales will also be derived: Negativity to assess the extent to which the respondent answers selected BRIEF items in an unusually negative manner and Inconsistency to assess the extent to which the respondent answers similar BRIEF items in an inconsistent manner. The Negativity scale is the number of items in 8, 13, 23, 30, 62, 71, 80, 83 and 85 with a score of 3, and so has a range of 0 to 9. A score of 4 or less is considered acceptable, 5 to 6 elevated and 7 or more highly elevated.

For the Inconsistency scale, there are 10 item pairs of related questions. The Inconsistency scale is the sum of the absolute values of the difference in scores for the items in each item pair, and so ranges from 0 to 20. The item pairs are questions 7 and 25, 11 and 22, 27 and 17, 33 and 32, 38 and 59, 41 and 65, 42 and 63, 44 and 54, 53 and 60, and 55 and 44. A score of 6 or less is acceptable, 7 or 8 questionable and 9 or more inconsistent.

BRIEF will be conducted at ScrV, EV (for DE and LTFU subjects respectively), at FEVs, YEVs and FV/EDV.

Change from Baseline in BRIEF scores (for raw scores and T-scores) will be calculated as:

Change from Baseline in BRIEF

= BRIEF score at postBaseline visit – BRIEF score at Baseline

at each visit in the Evaluation Period, if Baseline value is available. A change from Baseline < 0 indicates improvement and a change from Baseline > 0 worsening.

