3.10.5.3 BRIEF-P scores

The BRIEF-P is a questionnaire entered for subjects ≥ 2 to < 5 years of age to assess subjects' executive functioning. The questionnaire comprises 63 questions with entry options of N (never; scored as 1 point), S (sometimes; scored as 2 points), and O (often; scored as 3 points). Higher scores reflect poorer functioning. The questions are categorized in 5 components: Inhibit, Shift, Emotional Control, Working Memory and Plan/Organize. Additionally, three subscales will be used to calculate subscale scores.

The BRIEF-P form should be used for subjects ≥ 2 to < 5 years of age, with the following exception: for subjects who completed the BRIEF-P at Baseline assessment and turns 5 years of age between that assessment and the initial YEV, the BRIEF-P should be completed through and including initial YEV, and subsequently the BRIEF should be completed. Moreover, if a subject was below 2 years of age at Baseline but turns ≥ 2 years between Baseline and initial YEV, BRIEF-P will be assessed at visits after initial YEV.

Table 3–11 presents which questions belonging to which component and the constitution of subscales.

Table 3–11: BRIEF-P components and subscales

Scale/Index	Questions
Inhibit	3, 8, 13, 18, 23, 28, 33, 38, 43, 48, 52, 54, 56, 58, 60, 62
Shift	5, 10, 15, 20, 25, 30, 35, 40, 45, 50
Emotional Control	1, 6, 11, 16, 21, 26, 31, 36, 41, 46
Working Memory	2, 7, 12, 17, 22, 27, 32, 37, 42, 47, 51, 53, 55, 57, 59, 61, 63
Plan/Organize	4, 9, 14, 19, 24, 29, 34, 39, 44, 49
ISCI	All questions from Inhibit and Emotional Control
FI	All questions from Shift and Emotional Control
EMI	All questions from Working Memory and Plan/Organize
GEC Score	1-63

EMI=Emergent Metacognition Index, FI=Flexibility Index, GEC=Global Executive Composite, ISCI=Inhibitory Self Control Index

Standardized T-scores are determined from each subject's raw GEC, ISCI, FI, EMI, and component scores based on the subject's age and sex. Tables that map each raw score to the

appropriate T-score are provided in the BRIEF-P Professional Manual and will be reproduced programmatically.

Similar to analysis for BRIEF, the T-scores for BRIEF-P will be categorized using the legacy and the dichotomous approach to summarize categorical shift from Baseline. The same categorization as described in Section 3.10.5.2 applies.

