9.5 BRIEF-P and BRIEF assessment

The BRIEF-P/BRIEF assessments are completed at the ScrV (DE subjects only), FEV, YEV, FV, and at the EDV in the case of early discontinuation. For LTFU subjects (except those coming from core studies N01349, EP0065 and N01263), at the EV of N01266, the BRIEF-P/BRIEF score will be obtained from Baseline of the core study and should not be recorded in the eCRF for N01266. For DE subjects and LTFU subjects from core study EP0065, the Baseline BRIEF-P/BRIEF should be completed at the ScrV. As BRIEF-P/BRIEF questionnaires have not been recorded in core studies N01263 and N01349 and as this data was not collected at EV of N01266, no Baseline values are available for those LTFU subjects within N01266.

The BRIEF-P or BRIEF appropriate for each subject's age should be completed, with the following exception: For subjects who completed the BRIEF-P at the Baseline assessment and

turn 5 years of age between that assessment and the initial YEV, the BRIEF-P should be completed through and including the initial YEV, and subsequently the BRIEF should be completed.

Calculated T-score and raw score values and corresponding change from Baseline (if available) for the 3 indexed scores (Inhibitory Self-Control, Flexibility and Emergent Metacognition) and the GEC for the BRIEF-P questionnaire will be summarized for each visit during the Evaluation Period where the questionnaire is entered.

Calculated T-score and raw score values and corresponding change from Baseline (if available) for the 2 indexed scores (Behavioral Regulation and Metacognition) and the GEC for the BRIEF questionnaire will be summarized for each visit during the Evaluation Period where the questionnaire is entered.

In addition, for all indexed scores and GEC for BRIEF as well as BRIEF-P questionnaire, shift tables for T-scores will be done. These shift tables are based on T-score legacy categorization “Normal”, “Borderline” or “Clinical Significant” and the dichotomous approach “Normal” or “Potentially Clinically Significant” as described in Section 3.10.5.2 and Section 3.10.5.3 respectively and will summarize the shift from Baseline for each visit during the Evaluation Period where the questionnaire is entered. These shift tables will not include LTFU subjects from core studies N01349 and N01263 as Baseline values are not available from these studies,

All BRIEF-P and BRIEF assessment data (including validity scores negativity and inconsistency) will be listed.

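### The SAP grades a BRIEF or BRIEF-P T-score of 50 to <65 as Borderline in one shift table and Normal in the other, and the legacy cut at 50 leaves about half of a norm population outside Normal

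*SAP*

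**What the plan says.** SAP Section 3.10.5.2 states the purpose of the bands: "T-scores will be categorized with regard to CS to summarize categorical shift from Baseline". There are three of them in the legacy scheme. Scores below 50 are Normal, and scores of 65 or more are Clinically Significant. The band in between is set by the rule "If T-score is 50 - < 65 the CS category", and its label is Borderline.

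The dichotomous scheme follows in the same section and also concerns clinical significance. Its lower band is set by the rule "If T-score is < 65 then CS category", and its label is Normal. Scores of 65 and above are Potentially Clinically Significant.

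For BRIEF-P, Section 3.10.5.3 adds: "The same categorization as described in Section 3.10.5.2 applies". Section 9.5 puts both schemes to use: "In addition, for all indexed scores and GEC for BRIEF as well as BRIEF-P questionnaire, shift tables for T-scores will be done", on the legacy and on the dichotomous bands, at each Evaluation Period visit where the questionnaire is entered.

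The CBCL is handled differently. In Section 3.10.5.1 the legacy Normal band ends at 65, and the next rule, "If T-score is 65 - < 70 the CS category", opens the Borderline band there. The CBCL dichotomous scheme also ends Normal at 65.

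**The concern.** Within one section, the word Normal has two meanings for the same score on the same instrument. A child who moves from T = 48 to T = 52 goes from Normal to Borderline in the legacy table and stays Normal in the dichotomous one. The SAP does not say which table governs interpretation and gives no rationale for a boundary at 50. Having two schemes does not force this conflict: the two CBCL schemes agree on where Normal ends.

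The position of the boundary also matters. The SAP calls the scores standardized by age and sex. If the T-scale has its usual meaning, 50 is the average of the norm group, so an entirely average child sits on the edge of a band whose name suggests a clinical problem. Small movements around that point appear as changes in clinical-significance category. The study has one arm, so no control column shows how many such changes to expect without any drug effect.

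**Working it through.** **Inputs from the SAP.** Legacy cuts 50 and 65, dichotomous cut 65 (Section 3.10.5.2); same cuts for BRIEF-P (3.10.5.3). The SAP gives no figure for the share of subjects in each band or for expected shifts, so there is nothing to reproduce.

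**Assumptions, not in the SAP.** T is normal with mean 50 and SD 10 in a norm population, the usual convention; mean and SD are varied below. For shifts, the mean and SD are the same at Baseline and at the visit (no true change), with correlation r = 0.7, 0.8 or 0.9.

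**Step 1: labels side by side (needs no assumption).**

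| T-score | BRIEF legacy | BRIEF dichotomous | CBCL legacy | CBCL dichotomous |
|---|---|---|---|---|
| <50 | Normal | Normal | Normal | Normal |
| 50 to <65 | **Borderline** | **Normal** | Normal | Normal |
| 65 to <70 | Clinically Significant | Potentially Clinically Significant | Borderline | Borderline or Clinical Range |
| ≥70 | Clinically Significant | Potentially Clinically Significant | Clinically Significant | Borderline or Clinical Range |

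The BRIEF schemes disagree on what is Normal only in the row 50 to <65. The CBCL schemes do not disagree on Normal anywhere.

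**Step 2: share of a norm population in each legacy band.** With Φ the standard normal distribution function:

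- Normal: Φ((50 − 50)/10) = Φ(0) = 50.0%
- Borderline: Φ((65 − 50)/10) − Φ(0) = 0.9332 − 0.5 = 43.3%
- Clinically Significant: 1 − 0.9332 = 6.7%

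So 43.3% + 6.7% = 50.0% are not Normal. With the cut at 65 only, 6.7% are not Normal. Sensitivity of the legacy 'not Normal' share: SD 9 or 11, still 50%; whole-number scores, 52.0%; mean 48, 42.1%. If the trial mean is 55 it is 1 − 0.3085 = 69.1%, and if it is 60 it is 1 − 0.1587 = 84.1%.

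**Step 3: category changes with no true change.** Let P(i,j) be the bivariate normal probability of band i at Baseline and band j at the visit. The share changing category is 1 − Σ P(i,i).

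A check by hand for the cut at the mean: the share crossing 50 in either direction is 2 × [1/4 − arcsin(r)/(2π)]. For r = 0.7 this is 2 × 0.1266 = 25.3%. The legacy total adds those who cross 65 (7.7%) and counts once those who cross both cuts (about 0.5%): 25.3 + 7.7 − 0.5 = 32.5%, which agrees with the exact 32.6% up to rounding.

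| Mean T | r | Legacy (50 and 65) | Dichotomous (65) | Ratio |
|---|---|---|---|---|
| 50 | 0.7 | 32.6% | 7.7% | 4.2 |
| 50 | 0.8 | 26.8% | 6.4% | 4.2 |
| 50 | 0.9 | 18.9% | 4.6% | 4.1 |
| 60 | 0.7 | 36.5% | 22.2% | 1.6 |
| 60 | 0.8 | 30.0% | 18.0% | 1.7 |
| 60 | 0.9 | 21.3% | 12.6% | 1.7 |

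All percentages are of all subjects, in both directions. At mean 50, 12.4%, 10.2% and 7.2% of subjects go from Normal to Borderline by chance, and the same share goes back.

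**The case against.** The strongest reply is that the plan already contains the remedy. The scheme is labelled legacy, and Section 9.5 also provides the dichotomous tables at 65 and the T-score and raw-score changes. All summaries are descriptive, and BRIEF is an 'other' variable with an exploratory objective. The two BRIEF schemes are nested: the dichotomous one merges the two lower legacy bands, both put the clinical threshold at 65, and both can be programmed without ambiguity. All of this stands. It limits the harm to the legacy tables but does not remove the clash of labels or supply a reason for 50.

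It is also fair to say that these are children with epilepsy, whose mean may lie above 50. Above a mean of 57.5, midway between the cuts, 65 is the denser point. At mean 60, 14.9%, 12.2% and 8.6% of subjects cross 50 by chance, fewer than the 22.2%, 18.0% and 12.6% who cross 65. The contrast between the schemes then shrinks from about fourfold to about 1.6- to 1.7-fold. The legacy table still shows more movement, because it contains both cuts, and more children fall outside Normal.

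Two stronger readings are tempting, and the document supports neither. A reader might infer that Normal-to-Borderline shifts will mostly be measurement noise. The calculation assumes no true change, so it cannot say what share of observed shifts is noise. A reader might also infer that the shifts will be taken as drug-related cognitive worsening. That is a risk, not something the SAP says or plans. Any uncontrolled shift table, including the one at 65, has difficulty separating drug effect from background change.

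**Conclusion.** The point holds as a labelling and cut-point defect in the legacy BRIEF and BRIEF-P shift tables. The conflict over T = 50 to <65 is plain from Section 3.10.5.2 and rests on no assumption. The size rests on the conventional T-scale and on the assumed correlations: about half of a norm population is not Normal, and chance category changes are roughly four times as frequent as with the cut at 65 if the trial mean is 50, or about 1.6 to 1.7 times if it is 60. The direction is the same throughout the range examined. The consequence is modest: misleading clinical-significance labels in descriptive tables of an 'other' variable, alongside sounder summaries of the same data. It is still worth correcting before the tables are produced, because a single-arm report offers the reader no background rate against which to judge the shifts.

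**What to change.** Preferred: delete the three-level legacy categories for BRIEF and BRIEF-P from Sections 3.10.5.2 and 3.10.5.3 and the matching shift tables from Section 9.5, and rely on the dichotomous cut at 65, which is already planned, together with the T-score and raw-score changes.

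If the legacy tables are needed for comparability with earlier output, keep them as supplementary, state why 50 was chosen, and rename the 50 to <65 band so that it neither contradicts Normal in the other scheme nor implies clinical significance.

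Do not bring in the CBCL boundaries of 65 and 70. They belong to another instrument. Both BRIEF schemes set the clinical threshold at 65, and the CBCL bands would turn BRIEF scores of 65 to <70 from Clinically Significant into Borderline without any support in the SAP.

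The cost is SAP wording and a change of table format. No new data are needed. Dropping the tables gives up some comparability with earlier legacy output; the supplementary option keeps it.
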